## **13. ADDITIONAL MEASURES THAT MAY BE IMPLEMENTED BASED ON THE STUDY RESULTS AND CRITERIA FOR DETERMINATION OF THE INITIATION**

Review the risk management plan (RMP) including the following contents at the scheduled timing of milestones.

1. Review the necessity for changing the contents of this study plan including the presence or absence of new safety specifications.
2. Review the necessity for formulating risk minimization measures for new safety specifications.

## **14. SCHEDULED TIMING OF MILESTONES FOR EVALUATING IMPLEMENTATION STATUS AND OBTAINED RESULTS OR REPORTING TO THE PMDA, AND THEIR RATIONALES**

At the time of Periodic Safety Update Reports and the final evaluation of all-cases survey. To make a comprehensive review of the safety information.

## 15. OTHER NECESSARY MATTERS

### 1. Amendment of the full protocol

Based on the new knowledge to be obtained according to the progress of this study, the need for amendment of the protocol will be examined and the Full Protocol will be amended if necessary. Also, the need for amendment of the Full Protocol will be examined and the protocol will be amended when the partial change in the dosage and administration or indication is approved during the reexamination period (except when the reexamination period is newly designated), etc.

### 2. Actions to be taken for any problem or issue

Revision of the package insert and conduct of a new Post-marketing surveillance or new Post-marketing Clinical Trial should be considered for the following cases: any serious and unknown adverse reaction is suggested; a significant increase in the frequency of adverse reactions; any effectiveness or safety concern compared to pre-approval; rare adverse reaction is suggested.

## ANNEX 1. LIST OF STAND ALONE DOCUMENTS

None

1. AMENDMENTS FROM THE PREVIOUS VERSION

Version/ Date/ Author(s)/ Status of Study	Summary of Changes/Comments
1.0/ 21-June-2019/ PPD Before Enrollment	First edition
2.0/ 07-May-2021/ PPD Ongoing	
 2.1 The protocol amendments about the registration period and the patients who are subject to the investigation were reflected. 5.1 "No administration information - Administration information not determined" was added to the inclusion/exclusion criteria for the safety analysis set based on the Criteria for Inclusion Ver 2.0. 5.4 "Presence/absence of liver impairment" was added. 8.2.1.3 For the tabulation of discontinued patients, a time point at 30 months was added to allow determination whether the investigation period was prolonged due to concurrent treatment. 8.2.2.2 The tabulation of the total number of doses was changed to the tabulation of the number of doses per actual treatment period, and the tabulation of the dose per dose was changed to the tabulation of the dose per actual treatment period. The actual treatment period was defined as the treatment period excluding the non-treatment period. In addition, the statement that the treatment period would be tabulated as a categorical variable separately from its continuous variable was added. 8.2.3.3 For the analysis of adverse reactions by subgroup, the description about the range subject to calculation of risk ratios was modified, and tabulations of adverse reactions by SOC and PT for each subgroup for specific factors were added. 9 A listing of patients with adverse reactions for each safety specification was changed to a listing of adverse reactions for each safety specification. 10.1 A1.1 For the NYHA Functional Classification at baseline, the statement that the case report form should be referred to for the time point at the start of treatment was added because the date of evaluation was not collected. 10.3 The formula used to calculate mBMI was added. Other minor description modifications were made.

Version/ Date/ Author(s)/ Status of Study	Summary of Changes/Comments
3.0/ 21-April-2022/ PPD / Ongoing	
 • 2 and 2.2 A description about Vynmac was added. • 5.4 Gender was added as a factor for subgroup analyses for the safety evaluation. • 5.4 The factor “Dose change” for subgroup analyses for the efficacy evaluation was deleted (Because the effect to be truly evaluated will not be reflected by comparison of the presence/absence of dose changes if a temporary dose change is made frequently.) • 6.1 “Incorrect product selection between Vyndaqel and Vynmac” was added as an important potential risk in the safety specifications. • 8.2.2.2 A correction was made so that Vynmac can also be included in the tabulation of the administration status of this drug. • 8.2.3.3 A correction was made to include adverse reactions of Vyndaqel and Vynmac during the treatment periods before and after the switching to Vynmac. • 8.2.3 and 8.2.4 The statement that safety and efficacy will be evaluated using all data collected during the observation period without classifying the data into Vyndaqel and Vynmac unless otherwise specified was added. • Other minor description modifications were made.
4.0/ 08-June-2023/ PPD / Ongoing	
 • 2.1 Background information about a possible transfer to another hospital or department in this study was added. • 6.1 The name of the document separately describing the definitions of safety specifications was added instead of including descriptions of the definitions. • 7 The method of imputation of the end date of treatment in this study for patients continuing treatment with this drug was added. • 8.2.2.1 The periods for the use of concomitant medications and therapies to be tabulated were added. • 8.2.2.2 The method of tabulation of the administration records for transferred patients and the categorical variable of the initial dose were added. • 8.2.3.1.3 The number of days to onset and outcome were added to the tabulation of adverse reactions by item. • 9 A list of patients with adverse reactions in patients with variants was added. • 10 The REFERENCES section was added. • Other minor description modifications were made.

Version/ Date/ Author(s)/ Status of Study	Summary of Changes/Comments
5.0/ 28-May-2024/ PPD / Ongoing	
 • 2.1 The end date of the registration period was specified in association with the termination of registration only. In addition, the statement about registration only patients for investigation was deleted. • 5.1 The criteria for inclusion in the safety analysis set were added. • 5.2 The criteria for the efficacy evaluation in the efficacy analysis set and the description in the report were changed based on the latest version of the Guidance for Criteria for Inclusion in Analysis Sets and Data Handling in Use-result Surveys. • 5.3 The safety analysis set consisting of consented patients and the efficacy analysis set consisting of consented patients were added. • 5.4 Usage experience of this drug was added to and dose change was deleted from the subgroups. • 8.1.4 The method of handling a period data which includes interval-censored data was added. • 8.2 A description about the tabulation and analysis in the safety analysis set consisting of consented patients or the efficacy analysis set consisting of consented patients was added. • 8.2.1.1 The “Numbers of study sites and study patients by founder” section was deleted. • 8.2.1.1 The tabulation of patient disposition was changed from registered patients to patients with collected case report forms. • 8.2.2.1 The analysis sets for the breakdown of complications was changed to the safety analysis set only. In addition, the tabulation of the categories of concomitant medications was deleted. • 8.2.3 Adverse reactions and adverse events to be tabulated were changed from those occurring during the observation period to all of those collected. • 8.2.3.1.5 The “Relationship between concomitant medications and occurrence of adverse reactions” section was deleted. • 8.2.3.2.1 The “All adverse events” section was deleted. • 8.2.3.2.1 The section name was changed from “Serious adverse events” to “Adverse events by seriousness,” and the method of tabulation of non-serious adverse events was added. • 8.2.4.3 The period for the tabulation of the number and proportion of deaths was specified. • A1.1 The method of handling of multiple values of the same endpoint at the same visit time was added. • Other minor description modifications were made.

Version/ Date/ Author(s)/ Status of Study	Summary of Changes/Comments
6.0/ 23-Jan-2025/ PPD Ongoing	
 8.2.3.1.3 The tabulation of serious adverse reactions by outcome was added. 8.2.3.3 The subgroups to be tabulated for each SOC and PT were specified.

2. INTRODUCTION

This statistical analysis plan describes the statistical analysis plan for the special investigation of Vyndaqel or Vynmac (hereinafter, both drugs are collectively referred to as this drug unless otherwise specified). In this document, texts cited from the protocol are indicated in *italics*.

2.1. Study Design

Investigation period: March 2019 to September 2023 (From the start date of observation for the first subject to the end date of observation period for the last subject)

Registration period: March 2019 to March 2021 (From the start date of treatment for the first subject to the start date of observation period for the last subject)

Study patients: This study will be conducted with all patients surveillance system that all patients will be registered until data are collected on a target number of patients.

Target sample size: The number of patients with ATTR-CM in Japan is estimated to be approximately 750. Of these, the proportion of patients who actually received the definitive diagnosis and were prescribed with this drug was estimated to be approximately 40% (approximately 300 patients). As a result, the target sample size was set at 300 subjects from the viewpoint of feasibility. (300 patients to be evaluated for the safety of this drug)

Observation period: 30 months (Week 130) from the start of administration (Day 1). However, for patients who discontinued this drug during the observation period, the observation period will be until the first visit after the date of discontinuation.

Handling of patients transferred to another hospital or department: For the proper use of this drug, requirements for patients, institutions, and physicians have been specified by the Japanese Circulation Society¹, and it is necessary to meet all of these requirements to introduce this drug. However, since continued prescription at another institution is allowed in consideration of convenience, patients who have already started to receive this drug may be transferred to another hospital or department. If the patient is transferred to another hospital or department (hereinafter referred to as hospital transfer) during the observation period, the patient will be newly registered even at the transferred site and the CRF will be completed. If the patient is transferred to another hospital, the patient registration number of the original

site will be conveyed to the transferred site. Although the patient will be given a new patient registration number at the transferred site at the time of registration, he or she will be determined to be a transferred patient by reporting the patient registration number of the original site and his/her data will be handled as the same patient. However, registration is not necessary when the date of starting the treatment at the transferred site is on or after 01 April 2021. If the time point of 30 months after the start date of initial administration can be identified for the transferred patient, the observation period at the transferred site may be reset so that the total observation period of the patient in this study will become 30 months.

2.2. Study Objectives

The objective of this study is to comprehend information on the long-term safety (e.g., onset status of adverse reactions), etc. of patients who are treated with this drug for the treatment of ATTR-CM after the approval for the indication of this drug for ATTR-CM was obtained. When Vynmac is used, the study will be also conducted to grasp information on safety (e.g., onset status of adverse reactions), etc. during the observation period.

[Conditions for approval for Vyndaqel]

Because the number of study participants in Japan is very limited, the background information of patients using this drug* should be grasped by conducting a use-result survey in all patients while the data on a certain number of patients is accumulated after marketing and data on the safety and efficacy of this drug should be collected early to take measures necessary for proper use of this drug.

*: Vyndaqel

[Conditions for approval for Vynmac]

Because the number of study participants in Japan is very limited, the background information of patients using this drug** or Vyndaqel Capsules 20 mg should be grasped by conducting a use-result survey in all patients while the data on a certain number of patients is accumulated after marketing and data on the safety and efficacy of this drug or Vyndaqel Capsules 20 mg should be collected early to take measures necessary for proper use of this drug.

** : Vynmac

3. INTERIM AND FINAL ANALYSES

In this study, interim analyses for Periodic Safety Update Reports will be performed periodically. At the time of interim analyses, only the analyses necessary for Periodic Safety Update Report among the statistical analyses specified in this plan will be performed. In addition, the final analysis for the application for reexamination will be performed. At the time of the final analysis, all analyses specified in this plan will be performed.

4. HYPOTHESES AND DECISION RULES

This study is not a confirmatory investigation. Therefore, if a test is performed, an obtained result will be considered as exploratory.

4.1. Statistical Hypothesis

The p-value of test results will be evaluated as descriptive statistics. The significance level is not provided, but a threshold may be set afterwards for the purpose of screening.

4.2. Statistical Decision Rules

Not applicable.

5. ANALYSIS SETS

5.1. Safety Analysis Set

The safety analysis set is defined as the full analysis set that is as closer as possible to all patients treated with this drug. More specifically, the safety analysis set is defined as the population of patients registered or reported, excluding those who meet any of the following conditions:

1. The case report form could not be collected at all (Description in the report: "Case report form not collected")
2. There was a violation or deficiency in the contract (Description in the report: "Contract violation/deficiency")
3. There was a violation in the registration (Description in the report: "Registration violation")

Registration criteria: *The purpose of treatment with this drug is ATTR-CM. *Patients who have participated in clinical studies of ATTR-CM and are willing to continue receiving treatment of ATTR-CM are eligible for the registration.*

4. Administration of the drug under investigation is not reported at all (Description in the report: "No administration information")
5. Information on adverse events is not reported at all - No visits after the first prescription day (Description in the report: "No adverse event information - No revisits")
6. Information on adverse events is not reported at all - There is a visit after the first prescription day but no description of information (Description in the report: "No adverse event information - No description")
7. Information on administration is not reported at all (Description in the report: "No administration information - Administration information not determined")

The “Guidance for Criteria for Inclusion in Analysis Sets and Data Handling in Use-result Surveys” will be followed for the details of each criterion.

5.2. Efficacy Analysis Set

The efficacy analysis set is defined as the population of patients in the safety analysis set, excluding those who meet any of the following conditions:

8. Efficacy cannot be evaluated appropriately because of insufficient conditions for efficacy evaluation (Description in the report: “Efficacy evaluation not possible”).

5.3. Other Analysis Sets

5.3.1. Safety analysis set consisting of consented patients

Analysis population consisting of only the consented patients for the publication of results among the patients in the safety analysis set

5.3.2. Efficacy analysis set consisting of consented patients

Analysis population consisting of only the consented patients for the publication of results among the patients in the efficacy analysis set

5.4. Subgroups

Subgroup analyses of safety will be performed for the following patient characteristics and other factors. For the patient characteristics and other factors with those of specific categories underlined, a risk ratio will be calculated using each underlined category as the reference.

- Inpatient/outpatient status at the first prescription [inpatient, outpatient]
- *Severity of liver impairment [absent, mild, moderate, severe]
- Liver impairment [absent, present]
- Renal impairment [absent, present]
- Age [<15 years, ≥15 to <65 years, ≥65 years]
- *TTR genetic variant [wild-type, variant]
- NYHA functional classification [Class I/II, III/IV]
- NYHA functional classification [Class I, II, III, IV]
- Concomitant medication [absent, present]
- Non-drug therapy (device therapy) [absent, present]

- Complication [absent, present]
- Gender [male, female]
- Usage experience of this drug (administered this drug for the first time, transferred from clinical trials, transition from the treatment of ATTR-PN)

*Evaluation of the important missing information (safety in patients with severe liver impairment and patients with variants)

Subgroup analyses of efficacy will be performed for the following patient characteristics:

- TTR genetic variant [wild-type, variant]
- NYHA functional classification [Class I/II, III/IV]
- NYHA functional classification [Class I, II, III, IV]

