#### 8.2.1. Registration criteria

Patients must meet all of the following inclusion criteria to be eligible for inclusion in the study:

- The purpose of treatment with this drug is ATTR-CM.

\*Patients who have participated in clinical studies of ATTR-CM and continue to receive treatment of ATTR-CM are eligible for inclusion.

Refer to the latest package insert of this drug for “indications” and “dosage and administration” when this drug is administered. The descriptions on ATTR-CM are excerpted and shown below:

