#### **8.2.6. Observation period**

[figure not shown]
30 months (Week 130) from the start of administration (Day 1)

However, for patients who discontinued this drug during the observation period, the observation period will be until the first visit after the date of discontinuation.

[figure not shown]
In this study, information will be collected using a booklet type CRF. Information during the following periods will be entered in each booklet.

If the patient is transferred to another hospital or department (hereinafter referred to as hospital transfer) during the observation period, the patient will be newly registered even at the transferred site and the CRF will be completed. If the patient is transferred to another hospital, the patient registration number of the original site will be conveyed to the transferred site. Although the patient will be given a new patient registration number at the transferred site at the time of registration, he or she will be determined to be a transferred patient by reporting the patient registration number of the original site and his/her data will be handled as the same patient. If the time point of 30 months after the start date of initial administration can be identified for the transferred patient, the observation period at the transferred site may be reset so that the total observation period of the patient in this study will become 30 months.

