### 8.3.1. Patient characteristics

1. Enter the information at the start of administration of this drug into the registration form.

- a. Site information (if the study is conducted using paper CRFs)
- b. ID number
- c. Gender
- d. First day of treatment with this drug for ATTR-CM (first administration day of a marketed product of this drug for patients transferred from clinical trials, hereinafter the same)
- e. Identification of transferred patients (in the case of transferred patients, enter the patient registration number of the original site)
- f. Usage experience of this drug [administered this drug for the first time, transferred from clinical trials, or in treatment for transthyretin-type familial amyloid polyneuropathy (TTR-FAP) but also started to receive the treatment of ATTR-CM] (no entry is necessary for transferred patients)

If the patient is a transferred patient and the patient registration number of the original site has been entered, the entries for the following items g. to i. are not necessary (the entries are necessary even for the transferred patient if the patient registration number of the original site is not clear)

- g. Birth year (known at the start of administration of this drug) (if the birth year cannot be disclosed, enter the age at the start of administration of this drug)
  - h. Disease type of ATTR-CM (wild-type, variant, or unknown)
  - i. Severity of heart failure (NYHA Functional Classification)
2. The following will be recorded in CRF at the start of administration of this drug. If the contents of the registration form have been reflected, the investigator will check the contents again and make corrections as necessary.
- a. ID number
  - b. Gender

- c. Identification of transferred patients (in the case of transferred patients, enter the patient registration number of the original site)
- d. Usage experience of this drug (administered this drug for the first time, transferred from clinical trials, or in treatment for TTR-FAP but also started to receive the treatment of ATTR-CM) (no entry is necessary for transferred patients)

If the patient is a transferred patient and the patient registration number of the original site has been identified, the entries for the following items e. to o. are not necessary (the entries are necessary even for the transferred patient if the patient registration number is not clear)

- e. Birth year/age
- f. Inpatient/outpatient status
- g. Height (cm)
- h. Body weight (kg)

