### 8.3.8. Adverse events

Occurrence of adverse events from the start date of administration of this drug to the end date of observation period (or first visit date after the date of discontinuation of this drug) should be confirmed and the following information should be recorded.

Also, further investigation should be separately conducted, if deemed necessary by Sponsor for patients who experienced a serious adverse reaction, an unexpected adverse reaction or other adverse reactions not listed in the package insert.

- Presence/absence of adverse event
- Name of adverse event
- Date of occurrence
- Seriousness
- Change in the administration of this drug
- Intervention
- Outcome

- Causal relationship to this drug

If the adverse event is associated with abnormal laboratory values, i.e., clinical laboratory tests, the following information should also be recorded.

- Name of laboratory test
- Site reference value
- Unit
- Date of measurement
- Test results

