8.2.3.3. Exploratory analysis

For each of the factors specified in Section 5.4, the number and proportion of patients with at least one adverse reaction (incidence of any type of adverse reactions) will be tabulated, and for the incidence, the risk ratio among subgroups for each factor will be calculated as described in Section 8.1.3. However, after reconsidering the classification of a category with <10 patients, if calculation of a risk ratio is difficult, the

risk ratio to the category will not be calculated. In addition, unknown data will be excluded from the evaluation of risk ratios.

Serious adverse reactions and serious adverse events will also be analyzed in the same manner as above.

Adverse reactions will be tabulated by SOC and PT for each of the following subgroups:

- Liver impairment [absent, present]
- Renal impairment [absent, present]
- Age [<15 years, ≥15 to <65 years, ≥65 years]
- Pregnancy status [absent, present]
- NYHA functional classification [Class I, II, III, IV]

The onset status of adverse reactions will be evaluated for each product (Vyndaqel or Vynmac) during the treatment period until the first switching to Vynmac for Vyndaqel and during the treatment period after the first switching to Vynmac for Vynmac.

This drug is contraindicated to patients with a history of hypersensitivity to any of its ingredients. Because of limitations in evaluation in this study, no tabulation regarding contraindications will be performed. However, if hypersensitivity to any of its ingredients is reported as an adverse reaction, it will be presented in a listing.

Additional analyses may be performed as necessary. The exploratory analysis will be reported only when results giving important interpretation are obtained.

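### The wild-type versus variant safety ratio mixes first-time users with patients already taking the drug, so prior use may bias it, in a direction the documents do not settle

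*SAP*

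**What the plan says.** **The comparison.** Protocol 7.1 names use in patients with variants as one of two items of important missing information. SAP 5.4 lists TTR genetic variant among the safety subgroups and stars it with the note "Evaluation of the important missing information (safety in patients with severe liver impairment and patients with variants". For each factor in that list, SAP 8.2.3.3 says that "the number and proportion of patients with at least one adverse reaction (incidence of any type of adverse reactions) will be tabulated". It then asks for a risk ratio as in SAP 8.1.3, which gives a Wald interval with no adjustment or stratification.

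**The clock.** The registration form in Protocol 8.3.1 records "First day of treatment with this drug for ATTR-CM". Protocol 8.3.8 collects "Occurrence of adverse events from the start date of administration of this drug to the end date of observation period", and the observation period in Protocol 8.2.6 is 30 months.

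**Who enters.** Protocol 8.2.2 sets no exclusions, and two kinds of prior user are admitted:
- Protocol 8.3.1 has a usage-experience category for patients "in treatment for transthyretin-type familial amyloid polyneuropathy (TTR-FAP) but also started to receive the treatment of ATTR-CM".
- Protocol 8.2.1 states: "Patients who have participated in clinical studies of ATTR-CM and continue to receive treatment of ATTR-CM are eligible for inclusion". For them, Protocol 8.3 sets the first day of administration at the first day on marketed product.

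**What is done with prior use.** Usage experience is collected (Protocol 8.3.1), tabulated as a patient characteristic (SAP 8.2.2.1) and listed as its own safety subgroup (SAP 5.4). It is not crossed with genotype anywhere. Neither factor is among the subgroups for which SAP 8.2.3.3 tabulates reactions by SOC and PT.

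**The concern.** A prior user's record starts after some exposure has already been tolerated. Reactions during that earlier use fall outside the window, and people who stopped before Day 1 never enter. This is left truncation, and it is harmless to a comparison only if it affects both groups alike.

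Here it may not. TTR-FAP is familial by name, so patients who come from TTR-FAP treatment should all fall in the variant group. Protocol section 6 dates approval for TTR-FAP to September 2013 and for ATTR-CM to March 2019, so the earlier exposure could be long. A variant-to-wild-type ratio near 1 could then reflect who was already tolerating the drug rather than genotype. The separate usage-experience subgroup can show that prior users differ from first-time users, but it cannot correct the genotype contrast. At stake is how far the starred comparison informs a gap named in the safety specifications.

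**Working it through.** **The plan's own figure.** The documents give no figure for this comparison. The one probability they state is in Protocol 8.5.2: about 98% for at least 10 hepatotoxicity cases among 300 at 5.88%. The exact binomial tail is 0.984, so it reproduces. It concerns the whole cohort and does not bear on genotype.

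**Inputs.** From the documents: 300 patients in the safety set, a crude ratio, and the clock rules above. Not in the documents, and so assumed:
- *f*: share of variant patients who are prior users (from TTR-FAP treatment or trials)
- *g*: share of wild-type patients who are prior users (from trials)
- *k*: risk of a recorded reaction in a prior user relative to a first-time user
- the number of variant patients and the reaction risk

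The ratio is taken as variant over wild-type. SAP 5.4 marks reference categories by underlining, which the text available for this review does not show.

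**Bias.** Observed ratio = true ratio × [(1 − f) + f·k] / [(1 − g) + g·k].

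With k = 0.5 and g = 0, the multiplier is 1 − 0.5f:
- f = 0.2: 0.90
- f = 0.4: 0.80
- f = 0.6: 0.70

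A true ratio of 1.5 would then appear as 1.35, 1.20 or 1.05. Over f from 0.1 to 0.6 and k from 0.3 to 0.7, still with g = 0, it would appear as anything from 0.87 to 1.46.

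The other cases:
- g = f, any k: multiplier 1, no bias.
- k = 1, any f and g: multiplier 1, no bias.
- f = 0.1, g = 0.2, k = 0.5: 0.95/0.90 = 1.06, so a true 1.5 appears as 1.58. The bias has reversed.

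**Sampling error.** The Wald standard error of the log ratio at a true ratio of 1 and reaction risk r is √[(1 − r)/(r·n_v) + (1 − r)/(r·n_w)], with n_w = 300 − n_v. For n_v = 30:
- r = 0.10: √(0.9/3 + 0.9/27) = 0.577, interval 0.32 to 3.10
- r = 0.20: √(0.8/6 + 0.8/54) = 0.385, interval 0.47 to 2.13

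For n_v = 15 the intervals are 0.21 to 4.75 and 0.35 to 2.82. For n_v = 90 they are 0.48 to 2.10 and 0.61 to 1.64. The largest shift in the k = 0.5 example, to 0.70, lies inside all of them. The extreme corner (k = 0.3, f = 0.6, g = 0) gives 0.58, just outside the narrowest interval only.

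**First-time variant patients left.** Of 30 variants, 24, 18 or 12 remain at f = 0.2, 0.4 or 0.6. Of 15, 12, 9 or 6 remain, and the last two fall under the fewer-than-10 provision of SAP 8.2.3.3.

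**The case against.** A reader might infer that the risk in variants is understated and that the direction of bias is known. The documents do not support that. It needs two conditions they do not state: that prior users have fewer recorded reactions, and that they are a larger share of variants than of wild-type patients. Trial patients also enter with a reset Day 1, and nothing limits them to one genotype. A model that counts only TTR-FAP patients sets g to zero without saying so. This objection stands in full, and the conclusion is worded conditionally because of it.

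Further objections:
- **Exploratory role.** SAP section 4 says the study is not confirmatory and sets no significance level, and the ratio sits under exploratory analysis. This stands and limits the weight of the point. The comparison is nevertheless the one the SAP stars for the missing information.
- **Target population.** The objective concerns patients treated for ATTR-CM, so people who stopped during TTR-FAP treatment are outside it. That is right for describing the cohort. It does not make the two genotype groups comparable, because the selection may act on them unequally.
- **Already handled.** Usage experience is a subgroup and a tabulated characteristic, and Protocol 8.9 admits limited control of confounding. The one-way table shows a prior-use effect without removing it from the genotype ratio. Protocol 8.9 attributes the limitation to insufficient background data, whereas here both variables are collected.
- **Precision.** Sampling error probably exceeds the bias. This also stands, and it is a reason for a modest fix.

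**Conclusion.** The point holds in conditional form. The starred ratio is crude, it mixes first-time and prior users, and no planned analysis separates prior use from genotype. Prior use may therefore bias it, probably toward understating the variant risk if prior users have fewer recorded reactions and are commoner among variants. With equal prior-user shares, or no effect of prior use on reactions, there is no bias. If prior users with fewer reactions are commoner among wild-type patients, the variant risk is overstated.

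Every size is an assumption. The illustrative fall of 10% to 30% rests on half the recorded risk in prior users, none of them wild-type, and shares of 20% to 60% among variants. Against plausible intervals that is probably small. The conclusion also rests on reading TTR-FAP patients as variants, which follows from the disease name and is not stated as a rule, and on taking Day 1 from the registration-form definition. Protocol 10.2 starts safety reporting at the first dose of the drug. For a TTR-FAP patient that could be read as an earlier date, so the two passages should be reconciled.

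This is a worthwhile low-cost improvement to an exploratory analysis, not a defect that undermines the study.

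**What to change.** In SAP 8.2.3.3:
- Keep the all-patient wild-type versus variant figure.
- Beside it, give the same comparison restricted to the first-time-user category of usage experience. This removes both prior-user groups, so it works whichever way the bias runs.
- Tabulate adverse reactions by genotype crossed with usage experience, with denominators, so the mix is visible.

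In SAP section 9, add usage experience as a column in the listing of variant patients with adverse reactions.

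A Mantel-Haenszel ratio stratified by usage experience is not recommended as a substitute. The TTR-FAP stratum should contain no wild-type patients and would contribute nothing to the pooled estimate.

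**Cost.** SAP wording, two tables and one listing column, with no new data. The restricted comparison loses variant patients and precision. With 12 first-time variants, 270 wild-type patients and r = 0.20, the standard error is √(0.8/2.4 + 0.8/54) = 0.590 and the interval about 0.31 to 3.18, against 0.47 to 2.13 with all 30 variants. The wild-type group would also shrink if it includes trial patients. If the fewer-than-10 provision applies, the restricted table would show counts only.
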